****Updated to add changes in inclusionary criteria**

****Updated July 15, 2025 – Includes statistical analysis plan.**

Human Subjects Involvement, Characteristics, and Design

The study is a Phase I clinical trial that employs a randomized parallel design. We plan to enroll 160 children diagnosed with Developmental Language Disorder and their caregivers who will provide services to approximately half of these children. We predict that 15% of the children (N=20) will be lost to follow-up, thus we enroll 160, in order to have 140 children complete the entire study and meet the planned enrollment goals. Children will be randomly assigned to one of four treatment conditions, thus we expect 35 participants per condition. Research will be carried out at the University of Delaware and the University of Maryland College Park.

Children with Developmental Language Disorder (N = 160)

Inclusionary & Exclusionary Criteria:

- Age: 4-7 years old
- Primarily English speaking: Less than 20% exposure to another language, per parent report
- Document poor syntax skills: standard score below 85 on the DELV-NR composite, a dialect neutral assessment (Seymour, Roeper, de Villiers, & De Villiers, 2005).
- Nonverbal IQ within typical range: t-score at or above 35 on the DAS, matrices subscale, (Elliott, 2007).
- Hearing within the typical range: Pass screening using SoundScouts (Gumbie et al., 2018; Mealings et al., 2020) or provide reports of passing a hearing screening at school or in a pediatrician's office. *Due to COVID and limitations on in person activities, treatment may proceed even if these reports are not obtained if no one has concerns about hearing and we will track/follow up with families to obtain a clear hearing screening within 12 months of completion of intervention. Documentation of how many children did not complete hearing screenings will be retained and inform interpretation of data.
- No diagnosis of Autism: Cutoff score of 15 on the SCQ, (Rutter, Bailey, & Lord, 2003)
- No diagnosis of significant sensory-motor concerns or significant psychiatric disorders per parent report
- Able to benefit from treatment:
 - Score below 60% correct on experimenter developed elicited production probes of passives and object relative clauses
 - Producing simple transitive sentences (SVO) and MLU of 2.5 on 100 utterance language sample

Caregivers of Children with DLD (N=160)

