To guard against bias, children are randomly assigned to condition. A randomization scheme was pre-allocated at the beginning of the study by [name] at CRESP and uploaded to RedCap using a blinded allocation module. Allocation is requestable as children qualify for the study from CRESP. This ensures that the assessor at pre-test is blind to allocation. To ensure approximately equal allocation to each condition at each site, separate randomization schemes are used for each site. Flow through the study and drop outs at each phase are tracked following EQUATOR reporting guidelines.

Data Reduction

Estimated Dose

We compute estimated dose provided as follows:

$$\text{Dose} = \text{number of sessions reported by families} * \text{percent sessions documented based on recordings} * \text{recasts/sentences read verbatim observed in transcribed sessions}$$

Production Data

The dependent variable is production accuracy scored item by item as correct (1), incorrect (0), or unscorable (missing). Individual items are additionally coded as the syntactic type elicited (passive voice or object relative clause) and as treated/untreated clause type since that is counterbalanced across participants.

Eye-tracking Data

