We will also use generalized additive mixed models (GAMMs) to model longitudinal patterns in eyetracking data (i.e., looks to the agent) to examine and visualize timing of stimulus effects and changes in focus at key points during and after presentation of the prompt. GAMMs model fixations as an intensive time series (Cho et al., 2018, 2022) and allow identification of key points of separation. Moreover, the GAMMs models do not require prespecification of windows of time, providing more flexibility and sensitivity when modeling differences in eyetracking over time and between groups. The specification of the GAMMs models will mirror the GLMM equations below, except that smoothing functions will be used for an additional TIME predictor to fit a spline regression for each time series.

Aim 1. Determine the relative differences in the efficacy of illustrated syntax stories and recast therapy when treatment is dose controlled and delivered by highly trained SLPs in the laboratory.

We will first confirm that we achieved control of dose in the two in-lab conditions. We will carry out an unpaired two-tailed t-test comparing the estimated dose delivered for each condition. We anticipate that the two conditions will not differ and that the distributions will show high degrees of overlap ($p>.5$, $d<.3$).

To test the key question in Aim 1, we will compare the relative effect of treatment condition by testing for differences between the treatment effect estimates of stories in the lab and recasts in the lab conditions.

Well-matched groups at pretest will be evident if the two conditions do not differ at pre-test. If one treatment condition is more effective than the other, this should be evidenced by an interaction between test point and treatment contrast effects that are significant at the p<.05 level; if, as we hypothesize, the two conditions are equally effective there will be no significant interaction between test point and treatment. We are powered to detect an effect size difference of .35 (2 raw score points) or larger on production.

$$\begin{aligned} \text{Likelihood of a Correct Production} &= \text{TestPoint} * \text{TreatmentCondition} \\ &\quad + (1|\text{item}) + (\text{clause type} |\text{subject}) \\ \text{Structural Sensitivity} &= \text{TestPoint} * \text{TreatmentCondition} \\ &\quad + (\text{clause type} |\text{subject}) \end{aligned}$$

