$$\begin{aligned} \text{Likelihood of a Correct Production} &= \text{TestPoint} * \text{TreatmentCondition} * \text{EstimatedDose} \\ &\quad + (1|\text{item}) + (\text{clause type} |\text{subject}) \\ \text{Structural Sensitivity} &= \text{TestPoint} * \text{TreatmentCondition} * \text{EstimatedDose} \\ &\quad + (\text{clause type} |\text{subject}) \end{aligned}$$

In the event that the interaction between time point and treatment is not significant, we can directly test for treatment efficacy by comparing the effect of treatment on the treated or untreated structures. We expect that the model estimate for Treated vs. Untreated clause will be significant at p<0.05 level, favoring the treated clauses, demonstrating that treatment was effective and ruling out maturational effects.

$$\begin{aligned} \text{Likelihood of a Correct Production} &= \text{TestPoint} * \text{TreatedOrUntreated} \\ &\quad + (1|\text{item}) + (\text{clause type} |\text{subject}) \\ \text{Structural Sensitivity} &= \text{TestPoint} * \text{TreatedOrUntreated} \\ &\quad + (\text{clause type} |\text{subject}) \end{aligned}$$

Power Analysis for Production

Power analyses were carried out using Monte Carlo simulation (5,000 iterations) via SAS 9.4 and PROC GLIMMIX using residual pseudolikelihood estimation of a binary logistic mixed effects model with item responses (n=20) nested within tests (n=4 representing test point and clause type repeated measures) that are nested within children (n=120) who have been randomly assigned to treatment conditions, counterbalanced across the 2 clauses. Random effects are included for items within clauses, as well as four correlated child-level random effects (i.e., for each of the four repeated measures). A single model was used to estimate power in alignment with the overall design of the study in which children are randomly assigned to one of FOUR conditions. Power for the more focused models described above can be inferred from the power estimates for the treatment contrasts below. By adopting this randomization scheme and model design, we retain the ability to test unplanned contrasts that go beyond the planned analyses for the Aims if we so chose (e.g., recasts in the lab vs. recasts at home) in order to carry out secondary analysis associated with cost effectiveness, dose, or home environment.

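### The dose-free treatment contrasts estimate a separate pre-test mean per arm and judge matching by a comparison that cannot show it; a common randomised baseline would be at least as precise

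*Protocol*

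**What the plan says.** Under Randomization, "children are randomly assigned to condition", with a separate scheme per site. Allocation can be requested once a child qualifies, and of this arrangement the protocol says: "This ensures that the assessor at pre-test is blind to allocation".

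Under Analytic Approach, Aim 1, both production accuracy and Structural Sensitivity are modelled as `TestPoint * TreatmentCondition` with a child-level clause-type effect (plus an item effect for production). The asterisk brings in the main effect of condition, so the pre-test mean is free to differ by arm. Superiority of one treatment is to appear as an "interaction between test point and treatment contrast effects that are significant at the p<.05 level". Before that comes the matching criterion: "Well-matched groups at pretest will be evident if the two conditions do not differ at pre-test". The same sentence recurs under Aim 2, where the written model also multiplies in estimated dose.

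The document nowhere uses a common pre-test mean or the pre-test as a covariate. Its opening note says that it includes the statistical analysis plan, and the equations are written out, so this is a stated choice and not a detail left open.

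**The concern.** When arms are formed at random and the pre-test is scored blind, their expected pre-test scores are equal. A model that still estimates one pre-test mean per arm does not use that fact. It subtracts the full observed pre-test gap from the post-test gap, whether or not the pre-test predicts the post-test one for one. The result is unbiased but can be noisier than an estimate that shares the baseline or regresses on it.

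The matching sentence has a different fault. The absence of a detected difference between two small groups says little about how alike they are. A sizeable chance gap would usually be reported as good matching.

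At stake is precision. Power for stories at home against parent recasts is stated as only .75, and for Structural Sensitivity the protocol has no estimate of change over time.

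**Working it through.** **Inputs.** From Power Analysis for Production: pre-test SD s0 = 2.5; post-test SD on the treated clause s1 = 4.0 (both home arms) or 3.5 (both lab arms); pre/post correlation r = .90; post-test means 5.5 and 4.0 (home), 6.0 and 8.0 (lab). The power model has items and tests "nested within children (n=120) who have been randomly assigned to treatment conditions", that is 30 per arm. The design section has "thus we expect 35 participants per condition". From Power Analysis for Eye Tracking: Structural Sensitivity SD .17, with no pre/post correlation. Assumed: two-sided alpha .05.

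**The plan's own figure.** The stated .75 for the home contrast was not reproduced. Change scores give .81 in closed form: SE = √(2 × 4.25/30) = 0.532 and 1.5/0.532 = 2.82. Simulating the protocol's rounded, truncated scores gives .71. A logit mixed model fitted to those scores gives about .33. Between-clause correlation, item variance and contrast coding are not given, so the stated figure is not called wrong.

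**Per-child variance, raw scores.**
- Separate baselines (change): s0² + s1² − 2·r·s0·s1
- Common or adjusted baseline: s1²(1 − r²)
- Difference: (s0 − r·s1)², which is never negative

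| Contrast | r | Change | Adjusted | Reduction |
|---|---|---|---|---|
| Home | .90 | 6.25 + 16 − 18 = 4.25 | 16 × .19 = 3.04 | 28% |
| Lab | .90 | 6.25 + 12.25 − 15.75 = 2.75 | 12.25 × .19 = 2.33 | 15% |
| Home | .70 | 22.25 − 14 = 8.25 | 16 × .51 = 8.16 | 1% |
| Lab | .70 | 18.5 − 12.25 = 6.25 | 12.25 × .51 = 6.25 | 0% |
| Home | .60 | 22.25 − 12 = 10.25 | 16 × .64 = 10.24 | 0% |
| Lab | .60 | 18.5 − 10.5 = 8.00 | 12.25 × .64 = 7.84 | 2% |

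**Simulation of the protocol's rounded, truncated scores** (30 per arm, 6,000 runs):
- Home contrast without dose: SE 0.522 to 0.456 (variance −24%), power .71 to .82.
- Lab contrast: SE 0.481 to 0.439 (variance −17%), power .976 to .992.

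Both estimators give the same mean effect in each contrast (1.33 home, 1.95 lab), as expected of two unbiased methods.

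**Logit mixed model.** On data generated to follow that model (lab contrast, treated clause, unstructured pre/post child effects), a common baseline cut empirical variance by about 18% to 37%. Power rose from .60 to .73, .55 to .71 and .42 to .64 at latent correlations of 1.0, .9 and .6. Fitted to the protocol's own simulated scores, it lowered the model SE by about 9% to 13%, but the empirical SE did not fall reliably.

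**Structural Sensitivity.** With equal SDs the variances are 2s²(1 − r) and s²(1 − r²), so the reduction is (1 − r)/2: 35% at r = .3, 25% at r = .5, 5% at r = .9 (all assumed). At SD .17, 30 per arm and 80% power, the detectable difference goes from .123 to .106 at r = .5, and from .055 to .054 at r = .9.

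**The matching check.** At 35 per arm the SE of a standardised difference is √(2/35) = 0.239. A true gap of 0.3 SD is detected with power .24. An observed gap reaches p < .05 only beyond 1.995 × 0.239 = 0.48 SD, or 1.2 raw points at SD 2.5. Chance alone gives an observed gap of at least 0.3 SD in about 21% of randomisations (0.3/0.239 = 1.255). About 5% fall beyond the 0.48 SD threshold, so the other 16% would pass as matched.

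**Coding.** With two arms and two test points the planned fixed effects have rank 4. `TestPoint + TestPoint:TreatmentCondition` with TestPoint as a factor also has rank 4 and still holds an arm term at pre-test. With a numeric 0/1 post indicator the rank is 3, and the pre-test mean is shared.

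**The case against.** The strongest reply is that difference in change is a standard, unbiased analysis, and that the lab contrast, which is the Aim 1 question, already has raw-score power near .98. Both points stand.

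The larger figures also come from raw scores at r = .90, while production is analysed item by item on the logit scale. Twenty independent binary items with the protocol's means and SDs give observed correlations of only about .6 to .7, where the raw-score gain vanishes. This stands as a limit on the size. It does not reverse the direction of the raw-score result, since (s0 − r·s1)² cannot be negative.

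Some stronger readings are tempting and are not supported:
- *That the planned contrast is biased or invalid.* It is neither.
- *That dropping the arm terms costs nothing in Aim 2.* The written Aim 2 model conditions on estimated dose, which is observed after allocation and is expected to differ by arm (hypothesised medians 192 and 460). Randomisation does not equate arms at pre-test given dose. As an illustration, assume mean doses of 600 and 300, dose SD 250 and a dose–pre-test correlation of .2. At equal dose the arms then differ by .2 × (2.5/250) × 300 = 0.6 raw points at pre-test. The .82 does not belong to that model.
- *That the pre-test is stated to precede allocation.* Only assessor blinding is stated. Random allocation and blind scoring are what the argument uses.
- *That a significance test at pre-test is prescribed.* None is named. A non-significant comparison is the natural reading given the p<.05 language nearby, but no decision hangs on it.

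**Conclusion.** The point holds as one of efficiency for the randomised contrasts fitted without dose: Aim 1 production, Aim 1 Structural Sensitivity, and any home-arm contrast without dose. On raw scores at the protocol's own inputs the variance reduction is about 15% to 28%. That matters little for the lab production contrast and more for a home contrast stated at .75. At correlations of .6 to .7 the raw-score gain is essentially nil. For the planned logit model the evidence is mixed, and for Structural Sensitivity the gain depends on a correlation that the document does not give. The result rests on random allocation, blind pre-test scoring and pre/post child effects that are allowed to correlate.

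The matching criterion should go in both Aims whatever the size of the gain, because at these arm sizes a finding of no difference is weak evidence of similarity.

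**What to change.** 1. For the contrasts without dose, replace `TestPoint * TreatmentCondition` by a shared pre-test mean: `post + post:TreatmentCondition`, with post a numeric 0/1 indicator, and child effects at pre-test and post-test that may correlate. State the coding, because TestPoint as a factor restores the arm baseline. For Structural Sensitivity, post-test adjusted for pre-test is an alternative.
2. Leave the arm terms in the Aim 2 `TestPoint * TreatmentCondition * EstimatedDose` model.
3. Under Aims 1 and 2, delete the matching sentence and describe pre-test scores by arm instead.
4. Rerun the sponsor's production simulation with the shared baseline, so that the gain under the item-level logit model is known and not assumed.

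The cost is a little modelling work and one simulation rerun. No additional children or assessments are needed.

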A single caregiver will be identified at the time of enrollment to receive training in study procedures. In general, the caregiver's race will align with the child's race. Overwhelmingly women are the caregiver who coordinate this type of care, bring children to appointments, and engage in parent provided treatment. That said, we do not restrict this role to parents or to women. We will take care with our materials to encourage the participation of any primary caregiver.

Inclusionary & Exclusionary Criteria:

- Basic literacy skills per self-report
- Willing to participate in caregiver training and caregiver-based treatments if child is assigned to that condition
- Willing to participate in questionnaires and structured interviews during post-test

Study Procedures, Materials, and Potential Risks

Materials.

Screening and pre- and post-test materials will consist of commercially available standardized tests (see inclusionary and exclusionary criteria above) and experimenter developed probes. The experimenter developed probes will utilize illustrations that are child friendly to support the elicitation and comprehension of passives and object relative clauses.

Screening

After providing informed consent, parents will complete a case history form, the FOCUS questionnaire, the SCQ, and the BRIEF. An SLP or research associate will administer standardized and non-standardized assessments, including the DAS-2, matrices subscale, the DELV, the PPVT-5, the EVT-3, and a language sample. All information obtained will be coded with an alphanumeric code to protect confidentiality and stored on secure university servers. A 10-item elicited production probe will be completed at this point to determine if the child may advance to the pre-test stage.

Pre- & Post-Test

Children who qualify as DLD will be administered 2 20-item production probes to elicit passives and relative clauses. They will participate in a hearing screening. They will complete 2 blocks of 24-item comprehension probes (48 items total) to assess online comprehension of active/passive and object/subject relative clauses using a 2AFC eye tracking task administered via PClbex. Additional language sample data will be collected to ensure sufficiently large samples for analysis. Audio files, transcription, visual fixation data, and scoring will be coded with an alphanumeric code to protect confidentiality and stored on secure university servers.

Treatment

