Children will be randomly assigned to one of four conditions: recasts delivered by parents, recasts delivered by the clinician, syntax stories read by the parent, and syntax stories read by the clinician. In the recast condition, adults will interact with children and recast (restate, with a correction) a child's utterance as either a passive or object relative clause, with the goal of recasting 960 times over the course of the study (1 recast/minute, for 60 minutes, 16 sessions). In the syntax story condition, adults will read illustrated stories containing 30 exemplars of the target structure to children at least 32 times for a total of 960 exposures). These treatments will either be carried out by lab staff or by caregivers. During the treatment period, adherence, fidelity and language environment data will be collected using durable, long life audio recorders (LENAs) in conjunction with time logging/attendance records. In the home condition, training will be provided to the caregivers as to how to complete the treatment protocol via zoom. Caregivers will also be asked to log when treatment is carried out to focus the LENA analyses.

Assessment of the constructs within the Theoretical Domains Framework (TDF)

Motivation, self-efficacy, effort, and treatment efficacy will be assessed using rating scales administered to children (e.g., *how fun was today's session? how hard did you work today?*) clinicians (e.g., *how effective did you feel? how many times did you have to provide redirection?*) and caregivers (e.g., *does your child like coming to treatment? how effective did you feel today?*). These will be tailored to align with the treatment and delivery process. In addition, we will assess parent and clinician knowledge of the treatment through written tests of the grammatical targets and techniques used and observations of them providing treatment in the lab. Caregivers will complete a questionnaire designed to assess barriers within the TDF adapted from Huijg et al. (2014), see appendix. Finally, we will conduct structured interviews with parents during the post-test phase using an ethnographic interview style.

Risks

The primary risks associated with the study are loss of privacy or confidentiality, anxiety, and boredom and fatigue. The study procedures are entirely behavioral in nature and the risks do not exceed those experienced in everyday life. There is also the risk of being assigned to the less effective arms of the RCT.

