Second, for each time window (early and late), we will assess the extent to which Treatment Condition affects interpretation of the treated noncanonical structure. Our dependent variable will be **Structural Sensitivity**, calculated as *an averaged difference score of Agent Preference in the canonical structure (SRC, active) minus the noncanonical structure for each structure (ORC, passive) for each child.* This measure is selected rather than Agent Preference because it captures the **degree to which a child differentiates the two structures** from each other. Sensitivity to passive/object relative clause cues will be evident in values greater than 0, with higher values mapping onto increased sensitivity. Each child will receive a single Structural Sensitivity score for active/passives and a single Structural Sensitivity score for subject/object relative clauses at each test point.

Analytic Approach

For both comprehension and production outcomes, we utilize generalized linear mixed models to examine change over time for each condition. The adoption of generalized linear mixed models (GLMM) with random effects for subjects and items as the statistical approach has advantages in that we do not need to exclude children for failing to produce scorable responses given that this model can account for uneven response rates across children (Baayen, Davidson, & Bates, 2008) and it accounts for item level variance that can affect results.

Production probe accuracy will be analyzed with a logit link function. Use of a logit link function for production data also closely mirrors the underlying data structure in which individual items are scored as correct or incorrect. Structural sensitivity will be analyzed with linear mixed-effects models. Maximal models will include random intercepts (and possibly random slopes) for subjects, items, and clause type (Barr, Levy, Scheepers, & Tily, 2013), and parameter-specific p-values will be estimated with degrees of freedom determined through Satterthwaite approximation (Luke, 2017).

We will model comprehension and production outcomes separately, though we make similar predictions as to the effect of treatment on each outcome measure. Prior to carrying out the main analyses, we will check for differences attributable to participant sex and race (relevant biological variables). These will be included in future analyses if necessary, but prior work suggests that they are not likely to influence outcomes.

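### The Aim 1 and Aim 2 key models, as written, average treated with untreated clauses, and the fallback text names the wrong term of a correct equation

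*Protocol*

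**What the plan says.** **Design.** Under Treatment, the adult recasts the child's "utterance as either a passive or object relative clause". Under Pre- & Post-Test, all qualifying children "will be administered 2 20-item production probes to elicit passives and relative clauses". Production Data codes each item by clause type and also "as treated/untreated clause type since that is counterbalanced across participants". So every child supplies treated and untreated items at both test points.

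**Question.** Aim 1 is answered by "testing for differences between the treatment effect estimates of stories in the lab and recasts in the lab conditions". For comprehension, the Eye-tracking Data section states: "we will assess the extent to which Treatment Condition affects interpretation of the treated noncanonical structure". Power Analysis for Production gives gain to treated clauses only, and its dose simulation is checked against the treated structure.

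**Key models.** Under Analytic Approach, the Aim 1 fixed effects are TestPoint * TreatmentCondition, and Aim 2 multiplies these by EstimatedDose. The random part is (1|item) + (clause type|subject) for production and (clause type|subject) for Structural Sensitivity. TreatedOrUntreated appears in neither key model, and no sentence limits the data.

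**Reading of the result.** "If one treatment condition is more effective than the other, this should be evidenced by an interaction between test point and treatment contrast effects"; and "if, as we hypothesize, the two conditions are equally effective there will be no significant interaction between test point and treatment". The Aim 1 text adds: "We are powered to detect an effect size difference of .35 (2 raw score points) or larger on production".

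**Fallback.** If the interaction is not significant, both aims fit TestPoint * TreatedOrUntreated. The text expects the treated/untreated estimate to be significant and takes this as proof of efficacy and as excluding maturation.

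**The concern.** The equations and the question do not match. With no clause-status term, TestPoint x TreatmentCondition is the arm difference in gain averaged over the treated clause and one that is not expected to move. The same holds for the dose interactions in Aim 2. A tacit restriction to treated items does not fit the stated model: each child would then have one clause type, and a by-child clause-type effect could not be estimated.

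The direction matters. Aim 1 hypothesizes equal efficacy and reads a non-significant interaction as agreeing with it, so a diluted contrast leans toward the hypothesis. Power Analysis for Production also says that power for the focused models can be inferred from its treatment contrasts, which are built on treated-clause gains.

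The fallback has a smaller fault. A difference in gain between treated and untreated clauses is what excludes maturation. That is TestPoint x TreatedOrUntreated, which the equation contains but the text does not name.

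**Working it through.** **Inputs** (Power Analysis for Production): pretest M 3.0, SD 2.5, limited to 0-7, both clauses; untreated posttest M 3.0, SD 2.5; treated posttest 6.0/3.5 (stories, lab), 8.0/3.5 (recasts, lab), 5.5/4.0 (stories, home), 4.0/4.0 (recasts, home); pre-post correlation .90; 120 children, so 30 per arm with equal allocation. Two-sided 5% is assumed.

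**1. The plan's own power figures.** Gain variance = 2.5² + SD² - 2(.90)(2.5)(SD): 4.25 for SD 4.0, 2.75 for SD 3.5, and 1.25 for the untreated clause. Power ≈ Φ(difference/SE - 1.96).

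| Contrast | Stated | Treated gain | Treated minus untreated gain |
|---|---|---|---|
| Stories home vs recasts home (1.5) | .75 | .805 | .697 |
| Recasts home vs stories lab (2.0) | .90 | .985 | .945 |
| Recasts home vs recasts lab (4.0) | .99 | 1.00 | 1.00 |

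First row: SE = √(2 × 4.25/30) = 0.532; 1.5/0.532 = 2.82; power .805. The stated values lie near these but are not reproduced as a set. That shows no error, since the contrast, the between-clause correlation and the item variance are not given.

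**2. Size of the tested contrast.**
- Lab arms, treated gain: (8 - 3) - (6 - 3) = 2.0 points.
- Lab arms, averaged over clauses: (5 + 0)/2 - (3 + 0)/2 = 1.0 point.
- Home arms: 1.5 becomes 0.75.
- If a share g of the lab arm difference carried over to the untreated clause, the averaged contrast would be (2 + 2g)/2 = 1 + g. The protocol's inputs imply g = 0.
- Dose: mean gain per exposure is (.0005 + .006)/2 = .00325, or about .0016 when averaged with an untreated clause that dose does not affect.

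**3. Logit scale.** Two-arm binomial mixed models were fitted by pseudolikelihood to simulated scores (250 trials per setting, item variance set to 0 because none is given). The lab coefficient is 0.45-0.47 on treated items and 0.28-0.29 with the equation as written. So about 0.6 of it is kept, not one half.

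**4. Power, lab contrast.** Averaging also shrinks the SD, so power falls less than the effect. In closed form with independent gains:
- Treated: SE = √(2 × 2.75/30) = 0.428; 2.0/0.428 = 4.67; power .997.
- Averaged: SD = √(2.75 + 1.25)/2 = 1.0; SE = √(2/30) = 0.258; 1.0/0.258 = 3.87; power .972.

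Gain-score simulation with the stated rounding and limits (6000 trials per cell, 30-35 per arm, between-clause correlation 0, .5 or .8 assumed):

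| Reading of the scores | Treated only | Averaged | Loss |
|---|---|---|---|
| Observed totals | .97-.99 | .92-.96 | 3-5 points |
| Binomial(20) item noise added | .65-.73 | .45-.53 | about 20 points |

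The mixed models in step 3 gave .62-.70 against .39-.44. Their standard errors exceed the spread across runs, so they serve only to compare models.

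**5. Power, Aim 2 dose by test point** (doses from Table 1, full equation, gain-score version): 1.00 against .99-1.00 on totals; .80-.88 against .54-.62 with item noise.

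**6. Fallback.** Let G be the mean treated gain. Counterbalancing makes the expected pretest difference between treated and untreated clauses 0. The treated/untreated term then estimates 0 with pretest as reference, the time average G/2 with centred coding (up to scaling of the code), and G with posttest as reference. The interaction estimates G. For the lab arms G = (3 + 5)/2 = 4, or 3.9 after rounding and limits.

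| Quantity tested | Lab: mean, rejects | Home: mean, rejects |
|---|---|---|
| Pretest difference | 0.0, 5% | 0.0, about 5% |
| Time average | 1.95, 97-100% | 0.93, 44-98% |
| Posttest difference | 3.9, 100% | 1.85, 83-100% |
| Interaction (difference in gain) | 3.9, 100% | 1.85, 95-100% |

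**The case against.** **The intent is visible.** The eye-tracking text names the treated structure, similar predictions are made for production, and the power section works on treated gains. The key equations may simply lack a data restriction. That is fair, and a reader who infers that pooling was a deliberate choice goes beyond the text. But the equations are written out in a document that says it includes the analysis plan, and their random part points to both clauses.

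**The large power loss is not established.** A reader might infer that about 20 points of power are lost. That figure needs binomial noise on top of scores that read as observed totals. Added noise lowers the pre-post correlation from about .87 (after rounding and limits) to about .6 and puts about 7% of pretest scores above the stated maximum of 7. On totals, power as written stays at .92 or more for the lab contrast. This objection stands: only the direction of the loss is firm.

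**Halving is a raw-score result.** This also stands. The tested production coefficient is a logit and loses less.

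**The fallback is mostly wording.** A reader might infer that it cannot show efficacy. The documents do not support that: the equation holds the right interaction, the text introduces it as comparing treatment effects on the two structures, and centred coding would still detect the assumed lab effect. The near-zero result needs pretest-reference coding, which is not stated.

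**Other weaknesses should not be added in.** Reading non-significance as equal efficacy would remain a weakness in a treated-only analysis, and pooling does not inflate false positives when neither clause differs by arm.

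**Conclusion.** The point holds as a mismatch between the written key models and the question they are meant to answer. On the protocol's own inputs, with no arm difference on the untreated clause, the literal Aim 1 model tests a lab contrast of about 1 raw point where the power statement speaks of 2. The bias is toward no difference. Power is lower under every variant tried, but the amount is uncalibrated because neither item variance nor between-clause correlation is given.

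For Structural Sensitivity the dilution is one half only if the untreated structure does not change, and the protocol has no estimates of change. In the fallback the fault is confined to the sentence naming the estimate.

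The correction should be made before analysis. Otherwise the data set for the key test of both aims, and the term read in the fallback, remain open to choice after the results are seen.

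**What to change.** State in one sentence that the Aim 1 arm contrast and the Aim 2 dose interactions are tested on treated items only, and match the random part:

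- Production: TestPoint * TreatmentCondition [* EstimatedDose] + (1|item) + (TestPoint|subject).
- Structural Sensitivity: the same fixed effects with (1|subject), since only two scores per child remain.
- Fallback: name TestPoint x TreatedOrUntreated as the test of efficacy, and state the contrast coding.

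If both clauses are kept, add TreatedOrUntreated and its interactions with treated as the reference level. Read the treated-clause two-way terms (and their dose counterparts), not the added higher-order interaction, and recompute power. In the simulated lab-arm mixed models that added interaction had power of only .13-.18.

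The cost is a few lines of text, as clause status is already coded for every item. The interval for the arm contrast becomes about 1.6-1.7 times wider, for an effect about twice as large on the raw scale. A convergence fallback for the production model may also be needed.
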